### 2.1 Primary Objective

To evaluate Hi-VNI use for airway management and oxygenation in upper airway surgery from the anesthesiologist's and the surgeon's perspective with the specific focus on:

CONFIDENTIAL

This material is the property of the University of Pennsylvania.

- Physiologic changes during Hi-VNI use in apneic and spontaneously breathing patients such as maintenance of SpO2, changes in TcpCO2 (transcutaneous CO2) levels, and changes in vital signs, namely heart rate and blood pressure.

## **2.2 Secondary Objectives**

To collect clinical information about the effect of Hi-VNI use on procedure duration with the specific focus on:

- The effect of this technique on the duration of the induction phase of anesthesia, surgical procedure duration, and the duration of emergence from anesthesia
- Ease of use and any intra-operative and post-operative difficulties that may arise from use of this oxygenation technique

## **3 Investigational Plan**

### **3.1 General Design**

This is a prospective, interventional, pilot study that will describe the select cases of upper aerodigestive tract surgery performed at our institution with use of the Hi-VNI device. Data captured will be analyzed with a goal of determining the efficacy of this oxygenation technique for upper airway surgery. We will also collect useful clinical information about the most optimal clinical scenarios for use of this technique based on the cases in our data sample that will demonstrate successful case completion without a need for adjunct oxygenation techniques aside from Hi-VNI such as jet ventilation or endotracheal intubation.

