## Study Summary

Title	High Velocity Nasal Insufflation (Hi-VNI) Use in Upper Airway Surgery
Short Title	Hi-VNI Use in Upper Airway Surgery
IRB Number	834412
Methodology	Prospective, interventional, pilot study
Study Duration	1 year
Study Center	Single center (University of Pennsylvania)
Objectives	

• To establish the efficacy of Hi-VNI in upper airway surgery from the anesthesiologist's and surgeon's perspectives

• To describe the ideal patient and the ideal pathology as well as suitable clinical scenarios when Hi-VNI should be selected

Number of Subjects	100
Main Inclusion and Exclusion Criteria	
Inclusion criteria: Adult patients who are scheduled to undergo elective upper airway surgery at Penn.
 
Exclusion criteria: All patients with underlying medical conditions in which brief periods of hypoxemia or hypercarbia are not well tolerated will be excluded. Patients in whom delivery of air with oxygen via nasal passages is contraindicated will be excluded.
 

• Coronary artery disease

• Severe heart failure with EF < 40% or implanted ICD

• Pulmonary hypertension or pulmonary fibrosis

• History of increased intracranial pressure

• History of skull base or intracranial surgery

• Severe nasal obstruction

• Extremely low or extremely high BMI (BMI <16 or >40)

• Patients at high risk for aspiration

• Patients taken to OR for urgent or emergent upper airway surgery

Intervention	This study will involve use of Hi-VNI device as a primary or adjunct method for oxygenation.
Statistical Methodology	Mann-Whitney U test or Student's t-test and Kruskal-Wallis or ANOVA test will be used depending on the data distribution and the number of variables.
Data and Safety Monitoring Plan	The PI and sub-Is for this study will be responsible for the safety of the subjects enrolled into this study.

CONFIDENTIAL

This material is the property of the University of Pennsylvania.

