## 2 Study Objectives

The overall objectives for this study are to establish the efficacy of Hi-VNI in upper airway surgery from the anesthesiologist's and surgeon's perspectives, and to describe the ideal patient and the ideal pathology as well as suitable clinical scenarios when this oxygenation technique should be selected. This study will not change labeling of the Hi-VNI Precision Flow device by the Vapotherm and is not intended to change marketing claims of the manufacturer pertaining to this device.

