### Schedule of events:

### 3.4 Study Endpoints

#### 3.4.1 Primary Study Endpoint

The primary endpoint for this study will be case completion rate without alternative mode of oxygenation. In other words, for each case, the ability to complete the surgical procedure with use of only Hi-VNI device for oxygenation will be assessed.

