Using a normal end-tidal CO2 value of 37.5 mmHg and adding this value to the limits of the range of change in TcpCO2 listed above will give us a range of the values for TcpCO2 at the end of the procedure assuming the average duration of the procedure is  $22.5 \pm 4.5$  min. This range of the TcpCO2 at the end of the procedure would be [57.75; 67.88]. Our cutoff of TcpCO2 minus the baseline gradient between TcpCO2 and end-tidal CO2  $> 55$  mmHg is when the mode of oxygenation will be changed from Hi-VNI to an alternate method (endotracheal intubation or HFJV). The baseline gradient will be measured as the TcpCO2 minus the end-tidal CO2 during routine pre-oxygenation with a facemask. Based on the normal distribution assumption, one can deduce that only procedures with the duration one standard deviation away from the mean duration value of 22.5 min will not reach this level of TcpCO2. In other words, approximately 16% of patients will not require alternate means of ventilation (population which falls to the left of the line through a value of (22.5-4.5) on the normal distribution curve or 15.85%). Based on the author's prior experience and operative volume, there are 2-3 elective cases per week performed by the PIs that may qualify based on the inclusion/exclusion criteria to be included in the study. If 3 cases per week is used will equal to 144 qualified cases per year. For the confidence interval of 95% and the margin of error of 5% with the rate of 16%, the calculated sample size will equal to 86 individuals who might have a good chance of having their procedure completed with Hi-VNI without a need to switch to alternate mode of oxygenation. To account for the fact that some patients may not consent to be in the study or may require alternate means of oxygenation after Hi-VNI is used for other reasons, we added 14 patients to the sample size. This would lead to an estimated sample size of 100 individuals.

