## **6.3 Control of Bias and Confounding**

This is an interventional study that will involve recruitment of subjects who are scheduled to undergo an upper airway surgery and are good candidates for use of Hi-VNI during their procedure. The investigators for this study expect some degree of bias during the subject recruitment phase, but this selection bias will help exclude patients who will not tolerate use of Hi-VNI for oxygenation during surgery due to their co-morbidities. Please see Section 4.4 for exclusion criteria defined for this study.

CONFIDENTIAL

This material is the property of the University of Pennsylvania.

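### The only stated method for describing the ideal patient, pathology and scenario looks at cases that completed on Hi-VNI alone, and this cannot separate case mix from success rate

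*Combined protocol and SAP*

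**What the plan says.** - **Objective.** Section 2 sets out "to describe the ideal patient and the ideal pathology as well as suitable clinical scenarios when this oxygenation technique should be selected". The Study Summary lists the same aim. It does not reappear among the primary and secondary objectives in 2.1 and 2.2 or the endpoints in 3.4.
- **Method.** Section 3.1 says information on the best scenarios will be collected "based on the cases in our data sample that will demonstrate successful case completion without a need for adjunct oxygenation techniques". No other section gives a method for this objective.
- **Outcome.** The primary endpoint in 3.4.1 is "case completion rate without alternative mode of oxygenation", assessed case by case. Non-completers are therefore observed.
- **Analysis.** Section 6.2 lists two-group and multi-group tests (t-test or Mann-Whitney, ANOVA or Kruskal-Wallis) without naming groups or outcomes, and reports proportions as counts and percentages. Section 6.3.2 plans averages and standard deviations. Section 6.1 says there is no comparison or control group. Section 5.5 says, without a method, that everything captured will add to knowledge of ideal cases.
- **Who is in the sample.** Section 6.3 describes recruits who "are good candidates for use of Hi-VNI during their procedure". Section 5.4 lets the investigators discontinue subjects judged poor candidates before or during surgery, and 5.4.1 requires no further data on them. Section 3.2 admits Hi-VNI as either primary or adjunct technique.
- **Expected rate.** Section 6.1 expects that "approximately 16% of patients will not require alternate means of ventilation".

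**The concern.** To say when Hi-VNI should be selected, one needs the chance of completion given a feature: of all patients with this pathology, how many finished on Hi-VNI alone. A profile of completers gives the reverse quantity: of those who finished, how many had this pathology. A common pathology can dominate the successes simply because it is common, even when its completion rate is lower.

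Followed as written, 3.1 could therefore support a recommendation that the trial's own data contradict. The plan also expects non-completers to be the large majority, and they carry the denominators that the objective needs.

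**Working it through.** **1. The plan's own figure.** Inputs from 6.1 are a rate of 16%, a margin of 5%, 95% confidence and 144 qualifying cases a year.

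- Simple formula: n0 = 1.96² × 0.16 × 0.84 / 0.05² = 206.5.
- With a finite population correction at N = 144: 206.5 / (1 + 205.5/144) = 85.08, rounded up to 86.
- 86 + 14 = 100.

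The stated 86 reproduces with that correction, so this point does not rest on the sample-size arithmetic.

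**2. What a completer profile measures.** Let nA and nB be the cases enrolled with each pathology, and sA and sB their completion rates.

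Share of A among completers = nA·sA / (nA·sA + nB·sB)

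Equivalently, the ratio of A to B among completers is (nA/nB) × (sA/sB). Completers alone give the product. Recovering sA/sB requires nA/nB, which comes from all cases.

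**3. Illustrations.** Mixes and rates are assumed; the documents give none by pathology.

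| Cases A / B | Completion A / B | Completers A / B | Share of A among completers |
|---|---|---|---|
| 80 / 20 | 15% / 30% | 12 / 6 | 12/18 = 67% |
| 80 / 20 | 12.5% / 30% | 10 / 6 | 10/16 = 62.5% |
| 50 / 50 | 12.5% / 30% | 6.25 / 15 | 29.4% |
| 80 / 20 | 16% / 16% | 12.8 / 3.2 | 80% |

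- In row 1, A leads the successes although B completes twice as often.
- Row 2 shows the same reversal with the overall rate held at the plan's 16%, since 16/100 complete.
- Rows 2 and 3 have identical completion rates, yet the share of A falls from 62.5% to 29.4% because the mix changed.
- In row 4 completion does not vary, and the profile equals the enrolled mix.

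**4. What the full comparison could show.** At 16% of 100 the contrast is 16 against 84. The detectable standardized difference at 80% power, two-sided 0.05, is (1.960 + 0.842) × √(1/16 + 1/84) = 0.76. Power is about 45% for a difference of 0.5 and 84% for 0.8. At assumed completion rates of 10%, 30% and 50%, the detectable difference is 0.93, 0.61 and 0.56.

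For proportions, exact 95% intervals in row 2 are 6.2% to 21.8% for 10/80 and 11.9% to 54.3% for 6/20. Power to separate 12.5% from 30% with 80 and 20 cases is about 48%.

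**5. Sensitivity of the 16%.** Other inputs in 6.1 give fewer completers. From 37.5 mmHg at 1.125 mmHg/min, the 55 mmHg cutoff is reached at (55 − 37.5)/1.125 = 15.6 min. Under 22.5 ± 4.5 min, z = (15.6 − 22.5)/4.5 = −1.54, or about 6%. With 6 completers against 94, the detectable difference is about 1.18. The true rate is unknown, so the plan's 16% is a working figure only.

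**The case against.** The strongest reply is that this is under-specification in a descriptive pilot. Every case is assessed for completion. Section 6.3.1 summarises baseline characteristics without restriction to completers. Section 5.5 says all captured information will inform the ideal cases. With no control arm, the tests in 6.2 must compare groups from within the sample, and completers against non-completers is an obvious choice. Section 6.3 also acknowledges the selection of candidates openly.

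Much of this stands, and it rules out three stronger readings that a reader might infer:

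- **That only completers will be used and the other cases, about 84 at the plan's 16%, set aside.** Section 3.1 does not say only, 5.5 points the other way, and non-completers stay in the denominator of the primary endpoint.
- **That the completer profile merely describes who was enrolled.** In row 1 above, A is 80% of those enrolled but 67% of completers. The two coincide only when completion does not vary by feature.
- **That the design is at fault.** The outcome is assessed for every case; the gap lies in the analysis plan.

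The reply does not remove the point. Section 5.5 gives no method, 6.2 names no groups, and 6.3.2 offers averages and standard deviations. Enrolled and completer shares set side by side would recover the ratio of completion rates, but 6.3.1 does not say that pathology is summarised. The one explicit rule remains the one in 3.1, and it selects on the outcome. Calling the study a pilot does not help when an overall objective is to say when the technique should be chosen.

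**Conclusion.** The concern holds as a flaw in the stated method for one overall objective. Section 3.1 bases the description of ideal patients, pathologies and scenarios on completers, and such a profile cannot distinguish a common feature from a favourable one. No other section plans the comparison that would.

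The size of the distortion depends on the mix and completion rates by pathology, which the documents do not give. The illustrations show that a reversal is possible; they do not predict one. They also suppose that the most frequent feature among successes would be read as the ideal one, an interpretation the plan neither states nor prevents.

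The full comparison is feasible but exploratory. At the plan's 16% it can reliably detect only standardized differences of about 0.76 or more, and less if completers are fewer.

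**What to change.** Replace the clause in 3.1 with wording such as: *Suitable patients, pathologies and scenarios will be described among all cases started on Hi-VNI, by comparing those that completed on Hi-VNI alone with those that did not. The completion proportion and its 95% CI will be reported by pathology site, planned procedure type, BMI and age. This analysis is exploratory.* Cross-refer to it in 6.2.

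Four details need settling with it:

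- **Grouping factors.** Use baseline or pre-operative factors. Do not stratify by observed procedure length: under 3.3 a switch interrupts the procedure, so length is partly a result of the outcome. Use planned procedure type or expected length.
- **Denominator.** Count subjects discontinued from Hi-VNI during surgery (5.4) as non-completers, or report them separately. Keep the data needed to do so, despite 5.4.1. State how cases with Hi-VNI as adjunct (3.2) are counted.
- **Data items.** Record pathology site and procedure type for every case. Section 3.3 names age, sex, weight, height and BMI, but mentions pathology only through video review. Section 5.1 uses both pathology and planned procedure for eligibility, so they are known beforehand.
- **Scope.** State that conclusions apply only within the pre-selected population of 4.3, 4.4 and 6.3.

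The cost is a protocol edit, two recorded items and a few tables, with no change to conduct or sample size. The downside is wide subgroup intervals with about 16 completers in 100, so no firm claim about an ideal patient should be promised.

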### **3.2 Allocation to Interventional Group**

All subjects included in this study will undergo the same intervention, defined as the use of Hi-VNI as primary or adjunct oxygenation technique.

### **3.3 Study Measures**

After all of the eligibility criteria have been checked and a written informed consent has been signed by the patient, the recruited study participant's records will be reviewed and pertinent information about the patient's past medical/surgical history will be recorded, including age, sex, weight, height, BMI, and other relevant information.

All patients will receive preoperative evaluation according to the guidelines established by the American Society of Anesthesia (ASA). If according to the ASA guidelines the patient requires a pre-operative EKG or other testing, the testing will be conducted prior to arrival in the preoperative area for a scheduled surgery. This is a routine sequence of events for all surgical patients, where they receive a preoperative physical exam and evaluation needed for medical clearance prior to surgery. Each patient will be evaluated by the surgical and anesthesia teams as part of the routine sequence of events for any surgical patient. All patients will have a full set of vitals taken, and will be seen by the nurse, anesthesia and surgical teams in the preoperative area.

Standard anesthesia monitoring during surgery will include EKG, blood pressure, SpO2 measured using standard anesthesia equipment used at our institution, transcutaneous pCO2

levels (TcpCO2) measured using a SenTec transcutaneous monitor applied on the right or left upper arm prior to induction, EEG (using BIS monitor), and body temperature. We plan to use propofol and remifentanil without muscle relaxation as the primary anesthetic for all study cases. We do not define a maximum time for Hi-VNI use during the procedure. We anticipate that most of the study cases will be done within 20 minutes of the surgeon beginning the first step of the procedure. The anesthesia staff during the cases enrolled in this study will be limited to the sub-Is for this study (Drs. [name], [name], and [name]), who received an in-service training by the manufacturer of Vapotherm Precision Flow device, and have clinical expertise in use of this device in proposed settings. Both sub-Is are also familiar with the use of SenTec monitor during anesthesia, and will receive a detailed overview on how the device functions from a representative of SenTec before the study begins. They will be present in the OR during the study cases. Additional anesthesia team members including anesthesia residents, SRNAs and CRNAs will be required to read provided device manuals and study pathways/protocols before they participate in the care of the enrolled patients. The entire team including the circulator and the scrub tech, the surgical team, the anesthesia team will go over the use, the contraindications and hazards of the device use for Hi-VNI Precision Flow and SenTec monitor, the parameters that may prompt rescue ventilation and the steps to take if laser or cautery will be required. All staff members involved in the study cases will also review the airway fire protocol.

We intend to de-nitrogenate in the standard fashion with a face-mask. All patients will receive preoxygenation with bag-mask to ensure mask ventilation can be performed successfully during the case if needed and to determine end-tidal CO2. All patients who are successfully bag-masked during the induction phase will have disposable nasal cannula prongs placed to proceed with Hi-VNI use after the induction and the trial of bag-masking. If mask ventilation during the induction phase is successful, the anesthesia team will proceed with oxygenation via Hi-VNI device at a maximum rate of flow of 40 L/min and FiO2 of 100%. The rate of flow will remain at the maximum setting of 40 L/min throughout the case, and will not be adjusted at any point. If mask ventilation during the induction phase is unsuccessful, the anesthesia team will intubate the patient or HFJV will be initiated after exposure of the glottis by the airway surgeon as currently practiced, and this patient will be excluded from the study.

Transcutaneous CO2 is ideal for monitoring during apneic procedures with Hi-VNI since it provides a continuous trend of CO2 level and does not require a closed system (such as vent circuit attached to the endotracheal tube or a mask device). Prior studies reported no difference between transcutaneous CO2 levels and arterial CO2 levels during apneic procedures on the upper airway with Hi-VNI use and when the correlation between arterial and transcutaneous CO2 was measured in healthy volunteers. Transcutaneous CO2 correlated with arterial CO2 irrespective of BMI or sensor position further supporting its use in our study. Since the measurement of the transcutaneous O2 is still considered experimental, and its correlation with the patient's oxygenation state has not been described in the literature, we will not use this parameter in our study. Based on our initial clinical experience and the experience of our colleagues at other institutions with TcpCO2 monitor use during general

anesthesia, it is evident that end-tidal CO2 deviates from the level of TcpCO2 measured by the TcpCO2 monitor. We plan to establish a gradient between the value of end-tidal CO2 and the value of TcpCO2 in the beginning of each case, while the patient is being pre-oxygenated with a bag-mask. This baseline gradient will be used to determine the level of TcpCO2 adequate for continuous use of Hi-VNI during the case.

The Hi-VNI device will be used during the surgical procedure with continuous monitoring by anesthesia team. If at any point the SpO2 drops below 90% or TpCO2 minus the baseline gradient value rises above 55 mmHg, the airway surgeon and the anesthesiologist will stop the procedure and immediately switch to an alternate means of oxygenation by placing an HFJV cannula or a small-sized endotracheal tube through the laryngoscope into the glottis/trachea (a step performed in the beginning of the case if HFJV or endotracheal intubation are selected as primary methods of oxygenation during the case). These levels of TcpCO2 were not previously correlated clinically with PaCO2, and therefore should be avoided when using Hi-VNI system.

A total of 5 breaths will be administered via the endotracheal tube to determine the ETCO2 reading. If the ETCO2 reading is above 60 mmHg, the patient will be ventilated via the endotracheal tube. In other words, continuous monitoring will ensure that clinically significant hypoxia or hypercarbia (defined as SpO2 level below 90% or ETCO2 levels above 60 mmHg) that could eventually lead to adverse events if not promptly corrected will always be avoided by immediate switch to alternate means of oxygenation. HFJV equipment, a small-sized endotracheal tube, and all standard operating room airway and resuscitation equipment will be available as is the current standard during each case to allow for safe use of Hi-VNI and to prepare for the cases in which alternate means of oxygenation may be required.

All precautions will be taken to prevent vital sign changes that affect the accuracy of TcpCO2 measurements including changes in blood pressure, abnormal heart rhythm, or body temperature changes. Warming blankets will be used to avoid hypothermia. If a patient develops a transient arrhythmia or hypotension requiring vasopressor administration during the procedure, which can cause erroneous SpO2 and inaccurate TcpCO2, the patient will be intubated and the procedure will be completed with oxygenation/ventilation via the endotracheal tube. If the procedure cannot be performed with the endotracheal tube in place, the procedure will be aborted. If the arrhythmia persists, or if the nature of the arrhythmia is considered to warrant procedure termination, the procedure will be aborted. Additionally, if use of Hi-VNI support extends beyond 20 minutes, a blood sample will be drawn to evaluate CO2 level (PaCO2 or PvCO2). If the blood sample collection cannot be done, the patient will be intubated and ETCO2 will be measured.

[figure not shown]
If at any point during the procedure, a bleeding is encountered that requires cautery, the team will switch to an endotracheal tube to prevent aspiration of blood into the airway and to allow for appropriate hemostasis with use of cautery. If at any point during the procedure, it will become evident that the laser use is necessary, the team will switch to an alternate means of oxygenation. Standard practices currently in place to avoid airway fire will be used if the case demands use of electrocautery or laser. These practices will be implemented immediately once it becomes evident that either laser or electrocautery will be used. If laser or electrocautery will be used to control the bleeding during the case, following an endotracheal

[figure not shown]
intubation, appropriate washout of residual oxygen will take place per routine protocol, and the laser or cautery will not be used until FiO2 levels reach the values below 21%. All standard fire precautions will be used and the oropharynx will be suctioned to remove any potential residual oxygen excess. All cases will be screened prior to enrollment into the study to avoid inclusion of the cases with high risk of large-volume bleeding requiring cautery or with a need for laser use during the procedure.

Any upper airway procedure we perform begins with direct laryngoscopy and the exposure of the glottic airway with a laryngoscope. With the exposed view of the vocal cords/glottic opening, the exchange step of endotracheal intubation or placement of the HFJV cannula takes a few seconds. The surgical and anesthesia staff assigned to these cases are familiar with the exchange from one mode of oxygenation to another since this is commonly performed for these cases. After performing a portion or the entire case with HFJV, the team generally elects to intubate the patient for the final steps of the surgical case or for emergence from anesthesia. In cases where HVNI is used, the surgeon and anesthesiologist team will then decide if the patient will continue to receive oxygenation through the nasal cannula, get mask ventilated, or get intubated. Investigators for this study do not anticipate any additional risks to the patient or significant additional time needed to complete these procedures during this study, even in the cases where use of Hi-VNI alone is insufficient.

All surgical aspects of the case will be captured using video recording, which is standard for all upper airway surgeries at our institution performed with use of an endoscope or a microscope. A review of the video recordings for the cases included in the study will help us better understand how tubeless surgical space impacts the length of the case (from the time laryngeal exposure is visualized to the end of the case) and to visually document the airway pathology treated with Hi-VNI. The duration of induction, the procedure itself and the emergence from anesthesia will be measured. Post-operative recovery of each participant will be assessed from the standpoint of any airway related complications, prolonged drowsiness or other complications pertinent to this study. Additional information about the ease of Hi-VNI use and any difficulties encountered during the surgical case will be recorded. Patients will also be asked to rate the comfort of the procedure including sore throat and irritation, which is anticipated to be less with the HVNI technique.

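### Laser or cautery for bleeding after intubation must wait for an FiO2 strictly below 21%, a condition that washout with air cannot be shown to meet in practice

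*Combined protocol and SAP*

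**What the plan says.** All references are to the combined protocol and SAP.

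- Section 3.3 (Study Measures) runs Hi-VNI throughout the case: "oxygenation via Hi-VNI device at a maximum rate of flow of 40 L/min and FiO 2 of 100" percent.
- If bleeding during the procedure needs cautery, the same section has the team change to an endotracheal tube, in part "to allow for appropriate hemostasis with use of cautery".
- For laser or electrocautery used to control bleeding once the patient is intubated, it says that "appropriate washout of residual oxygen will take place per routine protocol", and that "the laser or cautery will not be used until FiO 2 levels reach the values below 21" percent.
- Section 10.1 (Risks) repeats these instructions almost word for word.
- Section 3.3 also has the whole team go over the steps for laser or cautery and review an airway fire protocol, which is not reproduced.

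The documents state no other FiO2 limit for this step, and no washout gas, tolerance, time limit or fallback.

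**The concern.** The condition is a strict inequality set at the whole-percent figure usually given for room air. The patient starts from 100% oxygen, and if the residual oxygen is washed out with air, FiO2 falls towards the oxygen fraction of air and no further. The stated limit then lies at that floor or a hair above it.

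This is an operative rule on which staff are briefed, for a bleeding patient who has just been intubated so that hemostasis can proceed. If the condition cannot be met, or cannot be seen to be met, the team must either hold back the cautery or depart from the protocol. Different teams may also settle on different unwritten limits. What is at stake is whether the instruction can be followed and whether compliance can be checked.

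**Working it through.** The plan gives no derivation of the 21% figure, so there is nothing to reproduce. The check is whether washout can bring FiO2 strictly below it.

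**Inputs**
- Starting FiO2: 100% (section 3.3).
- Condition: FiO2 < 21% (sections 3.3 and 10.1).
- Washout gas: not named. Assumed to be air.
- Oxygen fraction of air, A: not given. Assumed to lie between 20.9% and 21.0%.

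**Formula.** For simple single-compartment washout with time constant τ,

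F(t) = A + (100 − A) × exp(−t/τ).

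Setting F(t) = 21 gives

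t/τ = ln[(100 − A) / (21 − A)].

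**Results**

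| A assumed | Margin 21 − A (points) | (100 − A)/(21 − A) | Time constants to reach 21% |
|---|---|---|---|
| 20.9% | 0.10 | 79.1/0.10 = 791 | ln 791 = 6.67 |
| 20.95% | 0.05 | 79.05/0.05 = 1,581 | ln 1,581 = 7.37 |
| 21.0% | 0 | not defined | never |

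**Reading the table**
1. At 21.0% the washout floor equals the limit, so FiO2 never falls below it.
2. At 20.9% or 20.95% the condition is met only after near-complete washout. The remaining share of the starting gas must be under 1/791 = 0.13% or 1/1,581 = 0.06%. Residual or added oxygen that lifts FiO2 by the margin of 0.10 or 0.05 points cancels it.
3. In whole percent, 20.9% and 20.95% both read as 21%. A rounded reading of 20% would need FiO2 below 20.5%, which is under the floor across the whole assumed range.

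**The two instructions together.** The first intubates so that cautery can be used. The second withholds cautery until a condition is met that, under these assumptions, is either out of reach or not demonstrable at the precision in which the protocol states it. Nothing else in sections 3.3 or 10.1 resolves the conflict.

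**Effect on the endpoints.** A patient at this step is already on an endotracheal tube. The primary endpoint (section 3.4.1, completion with Hi-VNI alone) is therefore already not met, whatever happens with the cautery. Any wait could lengthen total case duration (section 3.4.2) in the cases concerned. No other figure in the statistical plan depends on the limit.

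**The case against.** The strongest reply is that the documents do not prove the limit impossible. They name no washout gas and give no oxygen fraction for air, and they leave the method to a routine protocol that is not reproduced. At 20.9% or 20.95% the condition is met in theory. A limit at or just under ambient oxygen also errs towards less oxygen at ignition. The wording may be a simple drafting slip that any clinician would read sensibly.

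Much of this stands. It is why the point is put as a condition that cannot be shown to be met, and not as a physical impossibility. It does not remove the point. The documents offer no means of going below room air, and the explicit figure governs use of the device, whatever the washout routine is.

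A reader might be tempted by four stronger readings that the documents do not support:

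- **That every laser or cautery use would be a deviation.** The sentence concerns laser or cautery used to control bleeding after intubation. Laser needed for another reason has its own instruction in section 3.3.
- **That many patients are affected.** Section 4.4 excludes pathology needing laser, pathology needing cautery throughout, and surgery with a high chance of heavy bleeding. Section 3.3 screens cases for the same risks before enrollment. The cautery in question is unplanned, and no bleeding rate is given.
- **That the repetition shows the figure was intended.** Section 10.1 is nearly a copy of section 3.3, so the second appearance adds no independent evidence.
- **That the rule has no protective value.** Its direction is cautious as to fire. The difficulty is delay or a technical deviation, and standard fire precautions apply alongside it.

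**Conclusion.** Wrong as written, as a decision threshold, and minor. If washout is with air at 20.9% to 21.0% oxygen, the strict limit is either never reached or met by at most about 0.1 percentage points. At whole-percent precision it cannot be shown to be met anywhere in that range. Taken literally, the fire-safety condition is set against the hemostasis step in the same section.

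The conclusion rests on three assumptions: that the washout gas is air, that its oxygen fraction lies in the stated range, and that FiO2 is read in whole percent, as the protocol writes it. The number of patients cannot be estimated from the documents but should be small. It would be wrong to infer a threat to the trial's results: primary endpoint status does not change, and at most the duration of a few cases could.

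**What to change.** The clinical team should reconcile the FiO2 condition in sections 3.3 and 10.1 with the cautery instruction in those sections and with the airway fire protocol to which section 3.3 refers. The stated condition should be one that can be met and verified at the precision of the monitor in use. Which value or rule to adopt is for the clinical team, and none is proposed here. Both sections should be changed together, since they now carry the same text.

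Recording FiO2 at each laser or cautery use would make compliance checkable, but it is optional, because no objective or endpoint needs it.

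The cost is one sentence in each of the two sections. Sample size and analysis do not change.
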